8.3.4. Clinical Safety Laboratory Assessments

All required laboratory assessments must be conducted in accordance with this protocol and the laboratory manual. The timing and frequency of laboratory assessments are specified in the Schedule of Activities ([Table 1](#) and [Table 2](#)).

- The laboratory tests (clinical chemistry, hematology, and coagulation) listed in [Table 8](#)) will be performed by the study centers' usual local laboratory.
- All laboratory reports will be filed with the source documents.
- Site personnel must enter results into the eCRF for the specified laboratory parameters (with units and relevant reference ranges) at each specified time point.
- The investigator must document their review of each laboratory report. Clinically-relevant abnormal laboratory findings at screening and before the first dose of study intervention will be recorded as medical history.
- Clinically-significant abnormal changes occurring during the treatment period of the study or within 42 days after the start of the last cycle of study intervention will be recorded in the eCRF as an AE(s). Clinically-significant abnormal laboratory findings are those that are not associated with the underlying disease, unless judged by the investigator to be more severe than expected for the participant's condition.
 - These laboratory tests will be repeated (and recorded in the eCRF) until the values return to normal or baseline or are no longer considered clinically significant by the investigator.
 - If such values do not return to normal/baseline within a period of time judged reasonable by the investigator, the etiology should be identified.
 - The investigator may consult with the medical monitor for any questions.

Laboratory tests may be performed at additional times during the study as part of standard care, as determined necessary by the investigator, or as required by local regulations. Any laboratory test(s) performed in response to an AE and any laboratory results that are used for decisions regarding participants' treatment response, study interventions, and/or AML treatments must be recorded in the participants' eCRF (as an unscheduled visit if not at a protocol-specified time point).

Refer to Section [5.2](#) for laboratory-related criteria for participant exclusion and Section [7](#) for laboratory-related criteria for interruption and discontinuation of study intervention.

Table 8: Laboratory Assessments

Laboratory Assessments	Parameters for Routine Monitoring	Additional Screening Parameters
Hematology	
 • Platelet Count • Hemoglobin • Absolute neutrophil count • White blood cell count with differential (unless count is too low) • Peripheral blast count • Blasts with Auer rods 	Screening only: Hematocrit, red blood cell (RBC) count
Clinical Chemistry	
 • Alanine aminotransferase (ALT) • Aspartate aminotransferase (AST) • Total and direct bilirubin • Alkaline phosphatase • Blood urea nitrogen • Creatinine • Lactate dehydrogenase • Calcium • Magnesium • Potassium • Sodium 	Screening only: Chloride, phosphate, albumin, total protein, glucose, uric acid, gamma-glutamyl transferase
Coagulation	
 • Activated partial thromboplastin time (aPTT) • Prothrombin time and international normalized ratio (PT/INR) 	Screening only: Fibrinogen, D-dimer

8.4. Adverse Events and Serious Adverse Events

AEs will be reported by the participant (or, when appropriate, by a caregiver, surrogate, or the participant's legally authorized representative).

The investigator and any qualified designees are responsible for detecting, documenting, and recording events that meet the definition of an AE or SAE and remain responsible for follow-up.

AEs will be categorized by system organ class and preferred term using the Medical Dictionary for Regulatory Activities dictionary and AE severity will be graded according to the National Cancer Institute-Common Terminology Criteria for Adverse Events (NCI-CTCAE).

8.4.1. Time Period and Frequency for Collecting AE and SAE Information

Any SAE that is considered related to study procedures will be collected from the time of consent until the first dose of study intervention. Any other medical occurrences that begin during this time period will be recorded on the medical history/current medical conditions section of the eCRF (not as an AE/SAE).

All AEs will be collected from the time of first dose through 42 days after the start of the last treatment cycle with study intervention (i.e., dociparstat or placebo administered during initial induction, reinduction, or consolidation therapy as specified in this protocol).

All SAEs will be recorded and reported to the sponsor or designee immediately and under no circumstance should this exceed 24 hours, as indicated in [Appendix 2: Adverse Events](#). The investigator will submit any updated SAE data to the sponsor within 24 hours of the data being available.

Investigators are not obligated to actively seek new onset AEs or SAEs after the protocol-defined reporting period; however, if the investigator learns of any SAE and he/she considers the event to be reasonably related to the study intervention or study participation, the investigator must promptly notify the sponsor.

8.4.2. Method of Detecting AEs and SAEs

The method of recording, evaluating, and assessing causality of AEs and SAEs and the procedures for completing and transmitting SAE reports are provided in [Appendix 2](#).

Care will be taken not to introduce bias when detecting AEs and/or SAEs. Open-ended and non-leading verbal questioning of the participant is the preferred method to inquire about AE occurrences.

8.4.3. Follow-up of AEs and SAEs

After an initial AE or SAE report, the investigator is required to proactively follow each participant at subsequent visits/contacts. It is important for all SAEs, AEs of special interest (as defined in Section [8.4.7](#)), AEs considered related to study intervention, and AEs that resulted in discontinuation of study intervention to be followed until resolution, stabilization, the event is otherwise explained, or the participant is lost to follow-up (as defined in Section [7.4](#)).

8.4.4. Regulatory Reporting Requirements for SAEs

Prompt notification of an SAE by the investigator to the sponsor is essential so that legal and regulatory obligations and ethical responsibilities towards the safety of participants and the safety of a study intervention under clinical investigation are met.

The sponsor has a legal responsibility to notify both the local regulatory authority and other regulatory agencies about the safety of a study intervention under clinical investigation. The sponsor will comply with country-specific regulatory requirements relating to safety reporting to the regulatory authority, Institutional Review Boards (IRB)/Independent Ethics Committees (IEC), and investigators.

Investigator safety reports must be prepared for suspected unexpected serious adverse reactions (SUSARs) according to local regulatory requirements and sponsor policy and be forwarded to investigators as necessary. An investigator who receives an investigator safety report describing an SAE or other specific safety information (e.g., summary or listing of SAEs) from the sponsor will review and then file it along with the investigator's brochure and will notify the IRB/IEC, if appropriate according to local requirements.

8.4.5. Death Events

If a participant dies during participation in the study (at any time from the time of consent through long-term follow-up), the investigator will provide the date of death and a determination of cause of death (including any supporting information, such as death certificate, pathology or autopsy information, as applicable).

All deaths from events with onset through 42 days after the start of the last treatment cycle with study intervention are to be reported as SAEs. Thereafter, the investigator will provide the requested information in the eCRF along with requested supporting information.

8.4.6. Disease-Related Events and/or Disease-Related Outcomes Not Qualifying as AEs or SAEs

The following disease-related events may be serious and life-threatening and are common in participants with AML:

- AML progression
- Thrombocytopenia
- Neutropenia

Because thrombocytopenia and neutropenia are typically associated with the disease under study, when the event(s) occurs with active leukemia, it is not to be reported by the investigator as an AE/SAE, unless the event meets one or more of the following conditions. If any of these conditions apply, then the event must be recorded and reported as an AE/SAE:

- The event is, in the investigator's opinion, of greater intensity, frequency, or duration than expected for the individual participant.
- The investigator considers that there is a reasonable possibility that the event is related to study intervention.

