
 To compare rates of hematopoietic stem cell transplant (HCT) after treatment with dociparstat plus chemotherapy versus chemotherapy alone. 	
 Proportion of participants who receive an allogeneic HCT during the study. Proportion of participants who receive any HCT (allogeneic or autologous) during the study.

 To compare relapse rates after treatment with dociparstat plus chemotherapy versus chemotherapy alone. 	
 Cumulative incidence of relapse after CR. Cumulative incidence of relapse after CR/CRi.

 To compare the time to hematologic recovery after induction or reinduction (if indicated) with dociparstat plus chemotherapy versus chemotherapy alone. 	
 Time to recovery of neutrophil count ($ANC >500/\mu L$ and $>1000/\mu L$). Time to transfusion-independent platelet recovery ($>20,000/\mu L$, $>50,000/\mu L$, and $>100,000/\mu L$). Incidence of prolonged neutropenia ($ANC \leq 500/\mu L$ past cycle Day 42 in the absence of active leukemia). Incidence of prolonged thrombocytopenia (platelets $\leq 50,000/\mu L$ past cycle Day 42 in the absence of active leukemia).
Other	

 To evaluate the consistency of dociparstat treatment effects across subgroups. 	
 EFS, OS, and MRD_{neg} across subgroups (e.g., age categories, genetic risk categories).

 To evaluate the pharmacokinetic (PK) profile of dociparstat. 	
 Dociparstat PK parameters, including area under the concentration-time curve (AUC), maximum observed concentration (C_{max}), time to maximum observed concentration (T_{max}), terminal elimination half-life ($t^{1/2}$), and clearance, and others as data permit.

 To evaluate the impact of dociparstat on medical resource utilization during induction and consolidation treatment. 	
 Number of days hospitalized. Number of days in intensive care unit setting. Number of blood product (packed red blood cells, platelets) units administered. Number of growth factor administrations.
Safety	

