
 To assess the safety and tolerability of dociparstat plus chemotherapy versus chemotherapy alone for the treatment of newly-diagnosed AML. 	
 Incidence of AEs: overall, treatment-related, Grade 3 or higher in severity, serious, fatal, and those resulting in treatment discontinuation. Incidence of AEs of special interest. Change from baseline in clinical laboratory parameters. Distribution of graded clinical laboratory results. Proportion of participants who meet defined QT/QTc criteria. Incidence of mortality at Day 30 and Day 60.

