8.4.7. Adverse Events of Special Interest

Adverse events of special interest, as listed below, must be recorded and reported to the sponsor (or designee) within 24 hours.

- Prolonged neutropenia:
Defined as a case of Grade 4 neutropenia that, in the absence of active leukemia, lasts past Day 42 of a chemotherapy cycle.
- Hemorrhagic AEs that are Grade 3 or higher in severity (per CTCAE criteria):
Additional information about hemorrhagic AEs will be collected to more fully describe the participant's status and assess potential causes and contributing factors; this includes, at a minimum, aPTT values, platelet values, possible contributory medications (e.g., heparin or other anticoagulants) in the preceding 7 days, and treatment(s) administered.

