9.4.4.1. Adverse Events

Treatment-emergent AEs (TEAEs) are those that begin on or after the date of the first dose of study intervention and on or before 42 days after the start of the last cycle of study intervention.

Summaries (number and percent of participants) of TEAEs (by system organ class and preferred term) will be provided as follows:

- All
- Severe, life-threatening, and fatal

- Treatment-related
- Severe, life-threatening, and fatal treatment-related
- Serious
- Treatment-related serious
- Those leading to study intervention discontinuation
- Those leading to study intervention interruption
- Fatal

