9.4.4.2. Laboratory Results

Descriptive statistics (N, mean, standard deviation, median, Q1, Q3, minimum, and maximum) will be provided for each continuous laboratory test as follows:

- Baseline values
- Values at each postbaseline analysis window (to be defined in the SAP)
- Change from baseline at each postbaseline analysis window

The minimum, maximum, and last postbaseline value / change from baseline will also be summarized. Missing data will not be imputed.

Laboratory tests will be descriptively analyzed by grade and analysis window using counts and percentages. The maximum and last postbaseline grade for each participant will also be summarized. Denominators will be the number of participants with a graded (or normal) test during the window. Laboratory tests with criteria for both increased and decreased levels will be analyzed for each direction (i.e., increased and decreased). This analysis will be generated twice to count (1) treatment-emergent increases in laboratory grades (i.e., only those above the baseline grade) and (2) any grade regardless of baseline.

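### Cytopenia TEAE percentages depend on leukemia response and cycles received, so if these differ between arms the tables can show a myelotoxicity difference at equal toxicity

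*Combined protocol and SAP*

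**What the plan says.** Section 8.4.6 treats neutropenia and thrombocytopenia as typical of the disease: "when the event(s) occurs with active leukemia, it is not to be reported by the investigator as an AE/SAE". There are two exceptions. One is an event judged "of greater intensity, frequency, or duration than expected for the individual participant". The other reads: "The investigator considers that there is a reasonable possibility that the event is related to study intervention". No comparable exclusion applies once leukemia is no longer active. Appendix 7 does not define active leukemia.

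Two related measures carry the same condition without the exceptions. The prolonged-neutropenia event of special interest in Section 8.4.7 is "Defined as a case of Grade 4 neutropenia that, in the absence of active leukemia, lasts past Day 42 of a chemotherapy cycle". The prolonged neutropenia and thrombocytopenia endpoints in Section 3 count only low counts "past cycle Day 42 in the absence of active leukemia".

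The safety endpoint in Section 3 is "Incidence of AEs: overall, treatment-related, Grade 3 or higher in severity, serious, fatal, and those resulting in treatment discontinuation". Section 9.4.4.1 implements it thus: "Summaries (number and percent of participants) of TEAEs (by system organ class and preferred term) will be provided as follows". The TEAE window closes 42 days after the start of the last cycle, so it lengthens with each cycle. Table 5 restricts consolidation, up to four cycles, to participants with CR or CRi.

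Section 9.4.4.2 does not filter on leukemia status: "Laboratory tests will be descriptively analyzed by grade and analysis window using counts and percentages". Times to neutrophil and platelet recovery (Table 7) are defined for all participants.

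**The concern.** Whether a given low count becomes an AE depends by default on whether the leukemia has cleared. Clearance happens after randomization, and study treatment is meant to influence it. Responders also receive further myelosuppressive cycles and stay longer in the TEAE window. A crude percentage of participants with a cytopenia TEAE thus mixes three things: toxicity per cycle, the share of participants whose cytopenias are reportable, and the number of cycles given.

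Section 2.1 expects the drug to improve outcomes with no added toxicity, and Section 2.3.1 lists myelosuppression among the risks. If response differs between arms, the cytopenia rows, and to a lesser degree the all, Grade 3 or higher and serious totals, can mislead in either direction. The DMC could see the same pattern, since Section 9.6 has it review safety data at the first interim analysis, where CR is also compared.

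**Working it through.** The plan gives no figure for this point, so there is nothing to reproduce. The check is an illustrative model in which true toxicity is identical and every participant becomes cytopenic.

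**Inputs from the plan**
- CR of 50% in both arms (Section 9.2).
- A CR difference above 30 points, one of three alternative routes to continuing blinded at the first interim (Section 9.5). The value 80% below is 50% plus 30 points.
- One induction cycle and up to four consolidation cycles (Table 5), so up to five cycles without reinduction.

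**Assumptions, not in the plan**
- p: share of participants whose leukemia is not active, with CR as a stand-in.
- r1 = 0.9: probability of a report when leukemia is not active.
- r0: probability of a report through the exceptions when leukemia is active, varied from 0 to 0.9.
- 60% clearance as an intermediate case.

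**Formulas**
- Reported rate = p × r1 + (1 − p) × r0.
- Artefact between arms = (p_drug − p_control) × (r1 − r0).

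Example with r0 = 0.3: control 0.5 × 0.9 + 0.5 × 0.3 = 60%; drug at 60% clearance 0.6 × 0.9 + 0.4 × 0.3 = 66%. The artefact is 0.10 × 0.60 = 6 points.

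| r0 | 50% cleared | 60% cleared | Artefact | 80% cleared | Artefact |
|---|---|---|---|---|---|
| 0 | 45% | 54% | +9 | 72% | +27 |
| 0.3 | 60% | 66% | +6 | 78% | +18 |
| 0.6 | 75% | 78% | +3 | 84% | +9 |
| 0.9 | 90% | 90% | 0 | 90% | 0 |

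- Planning case, 50% versus 50%: the first factor is 0, so the artefact is 0 for any r0.
- Reverse case, 50% in control versus 40% with drug: −0.10 × 0.9 = −9 points at r0 = 0, and −0.10 × 0.3 = −3 points at r0 = 0.6. An equal or somewhat higher true rate with the drug could be masked.

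**Cycles received.** With an assumed reporting probability q per reportable cycle, the share with at least one report after k cycles is 1 − (1 − q)^k. For q = 0.3 it rises from 30% at k = 1 to 1 − 0.7^5 = 83% at k = 5. For q = 0.5 it rises from 50% to 1 − 0.5^5 = 97%. These are within-arm figures. They create a between-arm difference only if the arms differ in cycles received. Part of the rise is real exposure to more cytarabine, but it is not a difference in toxicity per cycle.

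**The case against.** A reader might infer that an effective drug must look more myelotoxic, with AE totals inflated by construction. The documents do not support that.

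- The artefact needs a between-arm difference in clearance or cycles. Section 9.2 assumes equal CR and no separation of the EFS curves for 6 months, and Section 2.2 describes Phase 2b CR/CRi rates as broadly similar to control. A drug could improve OS and EFS with no induction-response artefact. The 30-point CR difference is one of three interim routes, not an expected effect.
- The exceptions are mandatory once met. Used freely, they remove the artefact. Against this, Section 11.2.3 requires positive grounds for a causal relationship, so how often they would apply during active leukemia is unknown.
- CR is an imperfect stand-in for leukemia not being active, because it also requires count recovery.
- Safety analyses are generally descriptive (Section 9.4.4), so no planned test is distorted. A serious cytopenia must also meet a seriousness criterion, and Section 11.2.2 excepts admission for routine transfusion. Infections and hemorrhages are not filtered.
- Unfiltered evidence already exists: graded laboratory tables, and recovery times tested in the fixed sequence of Section 9.4.3.

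All of this stands, and it limits the point to a conditional one. It does not remove it. Nothing in Section 9 says which source governs conclusions on myelotoxicity or warns the reader of the AE tables. The recovery endpoints cover induction and reinduction only, and maximum and last laboratory grade still depend on length of observation. The detailed SAP to which Section 9.4 defers, and the DMC charter, are not in the document reviewed, so any handling there could not be checked.

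**Conclusion.** The point holds in conditional form. Cytopenia TEAE percentages depend on response and cycles received, so a between-arm difference in either can produce or conceal a difference in reported cytopenia at equal toxicity. In the illustration the size runs from 0 (equal clearance, or exceptions used freely), through +3 to +9 points at 50% versus 60% clearance, to +9 to +27 points at 50% versus 80%. These ranges rest on assumed reporting probabilities, on CR as a proxy for cleared leukemia, and on cytopenia in every participant. They show possible size and are not forecasts. The matter affects interpretation of descriptive safety tables, with a partial check already in the plan, and is worth correcting because the correction is nearly free.

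**What to change.** In Sections 9.4.4.1 and 9.4.4.2, carried into the SAP and the DMC tables:

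1. State that between-arm conclusions on myelotoxicity rest on graded neutrophil and platelet counts irrespective of leukemia status, over a common induction window (for example Days 1 to 42), with consolidation shown separately, per cycle, among those treated.
2. Show neutropenia and thrombocytopenia TEAEs separately for induction and consolidation. Show the all, Grade 3 or higher and serious TEAE summaries with and without these terms, including the corresponding count-decreased terms.
3. Add a footnote that reported cytopenia AEs depend on disease status under Section 8.4.6.

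Section 9.4 finalizes the SAP before the first interim analysis, so the change belongs before then. The counts are already scheduled (Tables 1 and 2), and site AE reporting does not change. The cost is a few more descriptive tables. One limit remains: graded counts include cytopenia caused by the leukemia itself, and the consolidation tables compare responders only, so both should be read with that in mind.

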8.4.7. Adverse Events of Special Interest

Adverse events of special interest, as listed below, must be recorded and reported to the sponsor (or designee) within 24 hours.

- Prolonged neutropenia:
Defined as a case of Grade 4 neutropenia that, in the absence of active leukemia, lasts past Day 42 of a chemotherapy cycle.
- Hemorrhagic AEs that are Grade 3 or higher in severity (per CTCAE criteria):
Additional information about hemorrhagic AEs will be collected to more fully describe the participant's status and assess potential causes and contributing factors; this includes, at a minimum, aPTT values, platelet values, possible contributory medications (e.g., heparin or other anticoagulants) in the preceding 7 days, and treatment(s) administered.

8.5. Treatment of Overdose

For this study, any dose of study intervention (i.e., dociparstat or placebo) greater than 8 mg/kg as a bolus dose, greater than 0.5 mg/kg/hr infusion, or greater than 20 mg/kg within a 24-hour time period will be considered an overdose.

In the event of an overdose, the investigator should:

- Contact the medical monitor immediately.
- If the continuous infusion is ongoing, adjust the rate to administer the correct dose.
- Closely monitor the participant for any AEs/SAEs and laboratory abnormalities for at least 48 hours after the overdose.
- Document the quantity of the excess dose and the duration of the overdose in the eCRF.

Interrupt the study intervention infusion if clinically-significant bleeding (e.g., Grade 3 or higher hemorrhagic AE) or aPTT >45 seconds occurs after administration of an overdose of dociparstat (see Section 7.1). Other decisions regarding dose interruptions will be made by the investigator in consultation with the medical monitor based on clinical evaluation of the participant.

At the discretion of the investigator in consultation with the medical monitor, protamine may be used to neutralize the anticoagulation effects of dociparstat overdose. Protamine doses should be based on activated clotting time or aPTT plasma values and not based on the milligram dosage of dociparstat administered.

In the event of an overdose of cytarabine, idarubicin, or daunorubicin, refer to the approved product label(s) for guidance.

